Acceptance and uptake of COVID-19 vaccines will be instrumental to ending the pandemic, however, public confidence in vaccination is fragile, especially among racial and ethnic minorities. A recent nationally representative longitudinal study found that the public's likelihood of getting a COVID-19 vaccine declined from 74% in early April to 56% in early December 2020, despite the press releases in November 2020 of a high vaccine efficacy for 2 vaccines in phase 3 trials and the surge in cases during this timeframe.¹⁴ Likewise, self-reported likelihood of getting COVID-19 vaccination was lower among women, AA individuals, and those with lower educational backgrounds. Similarly, other studies have indicated that Latinx are less likely to trust the vaccine and that there is skepticism among Latinx communities across the country¹⁵ due to unequal access to health care, the lack of reliable information (especially in Spanish), coupled with disinformation.¹⁶ These findings highlight the mistrust between racial and ethnic minorities and public health officials, likely due to historical racism in health care and implicit bias.⁵ This is concerning due to their disproportionately higher burden from COVID-19 disease and because high levels of vaccination are necessary to reach herd immunity and control the pandemic. These findings emphasize the need for interventions that address these barriers and rebuilt trust in our communities of color. The proposed study is significant in that it will conduct extensive individual and community level awareness, education, outreach and health promotion that center on providing COVID-19 medically accurate and culturally competent information (in English and Spanish at 8th grade level) in order to empower our communities of color.

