access to COVID-19 vaccine, vaccine hesitancy). Additional measures at baseline and follow-up will be used as covariates (e.g., outreach and health communication, vaccine hesitancy or mistrust). Mean differences, both within and between treatment and control groups as well as group by treatment interaction effects will be analyzed. The targeted sample size is sufficient to detect a small effect size (.20) with power = .90 at alpha = .05 accounting for moderate participant attrition.

Descriptive Statistics. To describe the overall sample regarding demographics, structural and individual barriers, and potential covariates of intervention effects at baseline, prevalence statistics and means and standard deviation will be provided for all baseline variables; Cronbach's alpha of .70 will be required to be considered reliable. **Baseline Analyses to Detect Differences Between Treatment Groups.** Chi-square analyses and paired t-tests will be used to detect differences in demographics, knowledge of COVID-19 vaccine, access to COVID-19 vaccine, acceptance of COVID-19 vaccine and series completion, COVID-19 resource-seeking behaviors and linkage into care between intervention and control groups. Demographic variables included in these analyses will be age, gender, race/ethnicity, education, household income, marital status, and having insurance. Those variables differing across treatment groups at the $p < .20$ level will be included in subsequent adjusted outcome analyses. For the qualitative data analysis, final translated electronic transcripts will be imported into Dedoose. Analysis will be done through identification of recurrent themes following Crabtree and Miller's 5 step "interpretive process."¹⁹ First, transcripts will be read to identify common themes, codes will be developed and ~10% of data will be double coded and inter-rate reliability assessed. Coded text will be extracted and organized and read to identify emergent themes.⁶⁵ Matrices will be created to compare codes by themes (e.g., medical mistrust, discrimination, stigma, transportation, access to vaccination site, lack of insurance). Data will be utilized to refine *2VIDA!*, assess acceptability, and inform future vaccination efforts among underserved communities.

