Cover Page for ClinicalTrials.gov

Document: Statistical Analysis Plan

Official Study Title: Project 2VIDA! COVID-19 Vaccine Intervention Delivery for Adults in Southern California

NCT number: NCT05022472

Document date: February 5, 2021

STATISTICAL DESIGN AND POWER CALCULATIONS

We will approach overall data analyses using a multivariate repeated measures design (i.e., doubly multivariate) to assess mean differences in treatment and control groups on our primary (acceptance of COVID-19 vaccine and vaccine series completion) and secondary outcome variables (increased knowledge of COVID-19 vaccine, increased access to COVID-19 vaccine, vaccine hesitancy). Additional measures at baseline and follow-up will be used as covariates (e.g., outreach and health communication, vaccine hesitancy or mistrust). Mean differences, both within and between treatment and control groups as well as group by treatment interaction effects will be analyzed. The targeted sample size is sufficient to detect a small effect size (.20) with power = .90 at alpha = .05 accounting for moderate participant attrition. Descriptive Statistics. To describe the overall sample regarding demographics, structural and individual barriers, and potential covariates of intervention effects at baseline, prevalence statistics and means and standard deviation will be provided for all baseline variables; Cronbach's alpha of .70 will be required to be considered reliable. Baseline Analyses to Detect Differences Between Treatment Groups. Chi-square analyses and paired t-tests will be used to detect differences in demographics, knowledge of COVID-19 vaccine, access to COVID-19 vaccine, acceptance of COVID-19 vaccine and series completion, COVID-19 resource-seeking behaviors and linkage into care between intervention and control groups. Demographic variables included in these analyses will be age, gender, race/ethnicity, household income, marital status, and having insurance. Those variables differing across treatment groups at the $p < .20$ level will be included in subsequent adjusted outcome analyses.

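### Screened baseline variables enter the adjusted analyses on a p < .20 balance test that ignores clinic and prognosis; a fixed covariate list should replace it

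*SAP*

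**What the plan says.** The SAP paragraph on baseline analyses compares the arms on demographics, knowledge, access, acceptance and series completion, resource-seeking and linkage into care. The tests are ordinary participant-level ones: "Chi-square analyses and paired t-tests will be used to detect differences in demographics". The result decides the adjustment set: "Those variables differing across treatment groups at the $p < .20$ level will be included in subsequent adjusted outcome analyses". Protocol section 8 (Data Analysis) has the same rule. Neither document gives a prognostic criterion or a fixed list for these variables.

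The candidate demographics differ between the documents. The SAP has "Demographic variables included in these analyses will be age, gender, race/ethnicity, household income, marital status, and having insurance"; the Protocol has "Demographic variables included in these analyses will be age, gender, race/ethnicity, education, household income, marital status, and having insurance". Education is missing from the SAP list.

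A second route into the model has no p-value condition: "Additional measures at baseline and follow-up will be used as covariates (e.g., outreach and health communication, vaccine hesitancy or mistrust". The overall model is described thus: "We will approach overall data analyses using a multivariate repeated measures design (i.e., doubly multivariate".

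Protocol section 10 randomises clinics, three per arm, and the recruitment target is 500 participants per arm.

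**The concern.** A balance test asks whether the arms differ on a variable. Adjustment is useful when the variable predicts the outcome. A strong predictor at p = .21 is left out and an irrelevant one at p = .19 goes in, and nobody can write down the adjusted model before seeing the data. Protocol section 6 itself reports that "self-reported likelihood of getting COVID-19 vaccination was lower among women, AA individuals, and those with lower educational backgrounds", so the documents already hold some prognostic knowledge that the rule does not use.

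The tests also work at the wrong level. With six clinics randomised, ordinary differences between clinics appear as differences between arms. Imbalance need not be chance either: mini-vaccination stations, where participants are also recruited, exist only on the intervention side (Protocol sections 8 and 10). In addition, a paired t-test has no pairing to use when the arms are independent.

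At stake are a pre-specified adjusted estimate and whatever precision the prognostic covariates offer.

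**Working it through.** **Inputs from the documents.** 500 per arm in six clinics, so m = 1000/6 ≈ 166.7 per clinic; effect .20, power .90, alpha .05; six candidate demographics in the SAP.

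**Assumptions, because the documents are silent.** The effect is a standardised mean difference; tests are two-sided; 20% attrition where 400 per arm is used; ICCs, the covariate–outcome correlation r and the explained variance R² are as shown.

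**1. The plan's own power figure, unadjusted and ignoring clinic.** n per arm = 2(1.960 + 1.282)²/.20² ≈ 526. Power is .885 at 500 per arm and .807 at 400, so .90 is not quite reproduced two-sided. It can be recovered with inputs that are not stated, such as a one-sided test (429 per arm) or adjustment for a baseline covariate with r = .5 (526 × (1 − .25) ≈ 395 per arm). These figures serve only as reference values here.

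**2. Flag rate with independent participants.** With no true arm difference, a test at .20 flags 20% of variables whatever their prognostic value. Simulation gave .19 to .21 for r from .1 to .7. Of six demographics, 6 × .20 = 1.2 are expected to enter. If they are mutually independent, none enters in .8⁶ = 26% of trials.

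**3. Flag rate with six clinics and tests that ignore them.** DEFF = 1 + (m − 1) × ICC; flag rate = 2[1 − Φ(1.2816/√DEFF)].

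| Covariate ICC | DEFF | 1.2816/√DEFF | Flag rate |
|---|---|---|---|
| 0 | 1.00 | 1.282 | .20 |
| .01 | 2.66 | .786 | .43 |
| .02 | 4.31 | .617 | .54 |
| .05 | 9.28 | .421 | .67 |

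**4. Simulated power with independent participants, effect .20.**

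| Setting | p < .20 rule | Always adjusted |
|---|---|---|
| One covariate, r = .1, 500 per arm | .886 | .887 |
| One covariate, r = .3, 500 per arm | .901 | .915 |
| One covariate, r = .5, 500 per arm | .918 | .958 |
| One covariate, r = .5, 400 per arm | .844 | .910 |
| Six covariates, R² = .05, about 400 per arm | .825 | .823 |
| Six covariates, R² = .20, 400 per arm | .836 | .883 |
| Six covariates, R² = .30, 400 per arm | .832 | .916 |

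The gain is nil for weak covariates and about 4 to 8 points for strong ones.

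**5. True standard error with six clinics, outcome ICC .01.** Rule v always adjusted, one covariate with ICC .01: .0996 v .0988 (r = .3, ratio 1.008) and .0907 v .0890 (r = .5, 1.019). Six covariates, 133 per clinic: .101 v .099 (R² .20, 1.020) and .095 v .092 (R² .30, 1.033). The loss is about 1 to 3%. At covariate ICC .05 it is smaller for one covariate (.0970 v .0967; .0890 v .0877), because the rule then lets the covariate in more often.

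**6. Type I error.** With independent participants the rule is conservative: .036 at r = .5 and .029 at r = .7 (500 per arm); .039 and .036 for six covariates at R² .20 and .30. With outcome ICC .01 and no allowance for clinic, it is about .16 to .23 under either approach.

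**The case against.** The strongest reply is that little precision is lost. The plan has another route for covariates, and hesitancy or mistrust, named there, may predict vaccination better than any demographic. The repeated measures design can carry a baseline value of the outcome. In a clustered trial the screen passes many variables anyway, so the standard error suffers little (step 5). All of this stands and limits the size of the point. It does not supply a fixed model or make the balance test relevant. A clinic-level test at ICC .01 to .02 and R² .20 to .30 still favoured full adjustment by about 3 to 8 points, although total power there was only .23 to .41.

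A reader might infer several stronger things that the documents do not support:

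- *Covariates enter only through the p < .20 screen.* The unconditional covariates contradict this.
- *The trial adjusts for its own outcomes.* The outcomes are "primary (acceptance of COVID-19 vaccine and vaccine series completion", and both are on the screened list, but under a baseline heading. The survey records vaccination interest, hesitancy and uptake at baseline, and adjusting for a baseline outcome is ordinary ANCOVA. Deleting it could discard a strong predictor. A narrower concern remains: Phase I outreach, and the Resource Center that provides linkage at intervention sites only, may precede the baseline survey. Resource-seeking and linkage could then already reflect the intervention.
- *The screen inflates false positives.* By itself it makes the test conservative; the inflation comes from ignoring clinic.
- *The primary estimate is affected.* The documents do not call the adjusted estimate primary.
- *The precision is free.* The gain depends on unstated correlations, and for a yes/no outcome logistic adjustment changes the odds ratio being estimated.

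**Conclusion.** The point holds for the screened variables. Their entry into the adjusted analyses depends on observed imbalance, tested without regard to clinic, and is unrelated to prognosis. The 20% flag rate follows from the rule itself; 43 to 67% rests on assumed covariate ICCs of .01 to .05.

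The loss of precision is secondary and uncertain: from nothing to about 8 power points if participants were independent, and about 1 to 3% of the standard error at an assumed outcome ICC of .01. Always adjusting was as precise as the rule or more so in the settings run, apart from a .002 power difference at R² .05 that amounts to no gain either way. The case for change is mainly that the adjusted model should be known in advance. It is worth making before analysis, but a fixed list alone does not restore valid inference, which needs an analysis that accounts for clinic.

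**What to change.** In the SAP and in Protocol section 8:

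1. Delete the p < .20 rule. Baseline comparisons can stay as description.
2. Pre-specify one set of baseline covariates, kept whatever their p-values: age, gender, race/ethnicity, education, household income and insurance, plus the baseline value of the outcome where one exists. Reconcile the two lists on education. The documents link gender, race and education to vaccine intent; the other three are a judgement. Marital status, which is in both lists, may be added if that is decided in advance.
3. Fit the set in a model that accounts for the six randomised clinics (a clinic-level analysis has 6 − 2 = 4 degrees of freedom). Name the effect measure for yes/no outcomes and report the unadjusted estimate alongside.
4. Do not adjust for resource-seeking or linkage into care where these could already reflect Phase I. State when the baseline survey falls relative to Phase I, since the same caution applies to a baseline outcome recorded after exposure.
5. Do not adjust for any follow-up measure. Hesitancy is also a secondary outcome, and adjusting for its follow-up value may remove part of the effect.

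The cost is wording, because the variables are already planned for collection. The one practical burden is simple imputation for participants with a missing covariate.
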